#### **9.7.2.5.2 External Comparator Cohort Analysis**

Outcome prevalence for major congenital malformations in the erenumab-aooe exposed cohort will be compared with available external comparator cohort(s) representing the background prevalence of birth defects in the general U.S. population. The MACDP will be the main external comparator cohort ([MACDP, 2016](#); [NBDPN, 2010](#)). In the event any European data sources become available for descriptive comparison to this registry, the EUROCAT classification of congenital malformations would be implemented to ensure comparability.

The difference in prevalence of major congenital malformations in erenumab-aooe exposed cohort and the external comparator cohort will be compared similarly as to the internal comparator, with the estimate of risk ratio (95% CIs). Categorical distributions available in the MACDP report will be summarized using the same categories among erenumab-aooe exposed pregnancies ([CDC, 2008](#)). Indirect standardization methods will be applied for categorical distributions of maternal age, gestational age, and race/ethnicity. Indirect standardization involves calculation of the observed number of events (ie, major congenital malformations) and applying the maternal age, gestational age, and race ethnicity distributions from the reference population (ie, MACDP) to calculate the expected number of major congenital malformations. The ratio of the observed number of major congenital malformations to the expected number of major congenital malformations is referred to as the standardized prevalence ratio (SPR). Adjusted prevalence can be calculated by multiplying the SPR by the crude congenital malformation rate.

Published EUROCAT reports may be considered as an external comparator; the information would serve as a general non-U.S. population for comparison. Other possible comparisons with external datasets with adjustment methods (ie, direct or indirect adjustment with a standard population) for relevant available categorical

distributions (eg, maternal age, race/ethnicity, gestational age) as noted in [Section 9.9.2](#) will be explored at the time of final analysis. It is important to emphasize that any external comparator data source and women enrolled in this study are two distinctly different, thus “external adjustment methods” for inference comparisons are limited.

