**Table 2. Timing and Results of Prenatal Screening Tests: Key Descriptions**

Groups Determined by Test and Result	Inclusion in Analyses
Pre-enrollment prenatal screening: women who have already received prenatal testing where the result is known prior to enrollment	Variable based on subgroup
Subgroup 1: Women who have all normal findings	Included in primary analysis; included in sensitivity analysis of known test result(s) prior to enrollment
Subgroup 2: Women who have pregnancies with aneuploid disorders or genetic disorders that cause major congenital malformations	Excluded from primary and secondary analysis; analyzed as a separate group
Subgroup 3: Women who have pregnancies with results ( normal or abnormal) that are unrelated to aneuploid disorders or genetic disorders that cause major congenital malformations	Included in primary analysis; included in sensitivity analysis of known test result(s) prior to enrollment
Women who had no prenatal screening prior to enrollment in the registry	Included in primary analysis; exclude aneuploid or genetic disorders
Women who had prenatal screening after enrollment in the registry	Included in primary analysis; excluded in primary analysis women who have pregnancies with aneuploid disorders or genetic disorders that cause major congenital malformations

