**9.2.1.1 External Comparator Cohorts**

External comparators can provide additional context for study results, and will be used to descriptively characterize study results, with MACDP reports serving as the primary external comparator; representing the estimated underlying prevalence of major structural or genetic birth defects in the general U.S. population. Only aggregate, population-level data or published reports would be used for comparison. Further details of external comparator cohort analysis are in [Section 9.7.2.5.2](#).

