#### 9.2.1.1.1 Metropolitan Atlanta Congenital Defects Program (MACDP)

The MACDP, a population-based tracking system for birth defects, was established in 1967 as the first population-based system for the active collection of information about birth defects in the U.S. (MACDP, 2016). Currently, the MACDP tracking system captures approximately 35,000 births per year from 3 large metropolitan counties in the Atlanta area (5 counties were captured in earlier years). MACDP has monitored trends in birth defects rates and has served as a case registry for descriptive, risk factor, and prognostic studies of birth defects. Since 1998, MACDP surveillance has required that any signs or symptoms of a defect in the child be reported before their sixth birthday. In a 2007 report, the MACDP presented data on the prevalence and descriptive characteristics of birth defects, including 67 individual defects, in metropolitan Atlanta, Georgia, from 1968 to 2003 (Correa et al, 2007).

The frequency of birth defects is measured as prevalence at birth, expressed as the number of affected infants per 1,000 live births. Major structural or genetic birth defects affected approximately 3% of births in the U.S. (CDC, 2008). The prevalence estimates of stillbirth in 2006 and 2008 using MACDP data were 8.0 and 7.6 per 1000 live births plus stillbirths (95% CIs: 7.3, 8.7, and 6.9, 8.4), respectively (Duke and Gilboa, 2014).

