### **9.9.2 External Validity of Study Design**

To ensure internal comparability and where feasible, the internal comparator cohort will be recruited from the same clinical centers through HCP awareness and recruitment strategies (see [Section 9.2.1](#)) as the erenumab-aooe exposed pregnant women. However, the study population may not be reflective of the broader source population of pregnant women with migraine. Participation in the study is completely voluntary which may select for a particular type of patient group, such as women with severe migraine who have taken medication(s) “at-risk” due to the severity of their condition. Additionally, there are a wide range of treatments for migraine such that the distributions of migraine treatment exposures in the study may not be reflective of the treatment distributions in the source population, which could impact generalizability.

As there are no patient-level data available for the external comparator cohorts, there may be underlying differences between populations that are not detectable. However, reported categorical distributions of maternal age groups, race/ethnicity, or gestational age at birth, may be available for comparison to ensure baseline similarities to the registry population and external adjustment methods (ie, direct or indirect adjustment with a standard population) may be used.

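### The external comparison with MACDP misstates indirect standardization and uses different case definitions on its two sides; the net direction of the error is not established

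*Protocol*

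**What the plan says.** Comparing major malformations in exposed women with the general population is a secondary objective (Protocol Section 8.2), with MACDP as the main external source. Section 9.7.2.5.2 fixes the method: a risk ratio with 95% CI, and an SPR defined as observed over expected cases.

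- Variables: "Indirect standardization methods will be applied for categorical distributions of maternal age, gestational age, and race/ethnicity". Section 9.9.2 shows which gestational age is meant: "reported categorical distributions of maternal age groups, race/ethnicity, or gestational age at birth, may be available".
- Expected count: obtained by "applying the maternal age, gestational age, and race ethnicity distributions from the reference population (ie, MACDP) to calculate the expected number".
- Conversion back to a prevalence: "Adjusted prevalence can be calculated by multiplying the SPR by the crude congenital malformation rate".

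On the MACDP side, Section 9.2.1.1 takes the reports as "representing the estimated underlying prevalence of major structural or genetic birth defects in the general U.S. population". Section 9.2.1.1.1 gives the level, "Major structural or genetic birth defects affected approximately 3% of births in the U.S", says that the frequency is expressed per live births, and notes that since 1998 "MACDP surveillance has required that any signs or symptoms of a defect in the child be reported before their sixth birthday".

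On the registry side, Table 2 deals with women whose pre-enrollment testing showed an aneuploid or causative genetic disorder as follows: "Excluded from primary and secondary analysis; analyzed as a separate group". Its rows for women without earlier screening, and for those screened after enrollment, also take such disorders out of the primary analysis. The Abstract (Section 4, Data Analysis) and Sections 9.7.1.2 and 9.7.2.1 are narrower: they exclude disorders detected at first trimester screening. Malformations count up to 1 year of age (Section 9.7.1.2). Section 9.7.2.4 defines both a total prevalence, which includes cases in fetal deaths and terminations, and a prevalence at birth. Section 9.7.2.5.2 does not say which of the two enters the external comparison.

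**The concern.** Indirect standardization asks how many cases the registry would have had if its own mix of women carried the reference population's stratum-specific risks. The protocol's sentence brings in the reference population's mix instead and never mentions reference prevalences by stratum. A programmer following it could not produce a valid expected count.

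Two further elements of the same paragraph are doubtful. The SPR converts to an adjusted prevalence only when multiplied by MACDP's crude prevalence, and the text leaves the population unnamed. Gestational age at birth arises after exposure and may result from the malformation, so it is not a confounder to be standardized away.

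Apart from the formula, numerator and reference do not count the same thing. Genetic disorders leave the registry but stay in the MACDP figure, and no section aligns the two. At stake is the reading of a published ratio with a confidence interval in a registry that the FDA required. Section 9.9.3 also expects that low enrollment may weaken the internal comparison, so readers may lean on the external one.

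**Working it through.** **Number of births.** The protocol gives no figure for the SPR, so I use its planned 749 live births per group (Section 9.5, Table 4). That figure reproduces: 3% v 6%, two-sided 0.05, 80% power, pooled variance without continuity correction gives 749, and 749 / (0.85 × 0.62) = 1421.25, stated as 1421.

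**1. The expected count.** The correct form is E = Σ (registry births in stratum × MACDP prevalence in stratum). The strata below are assumed for illustration:

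- MACDP: 85% under and 15% over 35 years, with prevalence 2.80% and 4.13%. Crude: 0.85 × 2.80% + 0.15 × 4.13% = 3.00%.
- Registry: 65% and 35%. At MACDP rates: 0.65 × 2.80% + 0.35 × 4.13% = 3.27%.

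| Expected count from | E, true RR 1 | SPR, true RR 1 | E, true RR 2 | SPR, true RR 2 |
|---|---|---|---|---|
| Registry distribution × MACDP rates (correct) | 24.46 | 1.00 | 24.46 | 2.00 |
| MACDP distribution × MACDP rates | 22.47 | 1.09 | 22.47 | 2.18 |
| MACDP distribution × registry rates | 22.47 | 1.09 | 44.93 | 1.09 |

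Observed cases are 24.46 at RR 1 and 48.92 at RR 2. The second row is simply 749 × crude MACDP prevalence, so age has not been adjusted for. The third row compares the registry with itself and cannot show a doubling. The sign depends on the age mix: if the two distributions are exchanged, so that the registry is the younger population, the second row at RR 1 gives 22.47 / 24.46 = 0.92.

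**2. The crude-rate multiplier.** At true RR 2, the correct SPR × MACDP crude is 2.00 × 3.00% = 6.0%. Multiplying by the registry's own crude rate would give 2.00 × 6.53% = 13.1%, which counts the effect twice.

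**3. Gestational age.** Assume 3% malformations, and preterm birth in 10% of unaffected and 25% of affected infants.

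- Reference preterm share: 0.03 × 0.25 + 0.97 × 0.10 = 10.45%. Malformation risk is 0.0075 / 0.1045 = 7.18% if preterm and 0.0225 / 0.8955 = 2.51% if term.
- At true RR 2 the registry's preterm share is 0.06 × 0.25 + 0.94 × 0.10 = 10.9%. The expected risk is 0.109 × 7.18% + 0.891 × 2.51% = 3.02%, so SPR = 6 / 3.02 = 1.99. With 20% to 30% preterm among affected infants the range is 1.99 to 1.98, which is negligible.
- If the registry's preterm share is higher for other reasons, a true RR of 1 shows as 0.96 (share × 1.24) or 0.92 (share × 1.5). The factor 1.24 borrows the preterm-birth odds ratio for migraine in Section 7.2; 1.5 is assumed.

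**4. Genetic defects.** Let g be the share of MACDP cases that are genetic. The protocol does not give it; I assume 5% to 25%. The all-defect reference expects 749 × 0.03 = 22.47 cases. If every such case leaves the registry, a drug with no effect yields 22.47 × (1 − g) cases, so SPR = true RR × (1 − g).

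| g | Cases if no effect | SPR, true RR 1 | SPR, true RR 2 |
|---|---|---|---|
| 5% | 21.35 | 0.95 | 1.90 |
| 10% | 20.22 | 0.90 | 1.80 |
| 20% | 17.98 | 0.80 | 1.60 |
| 25% | 16.85 | 0.75 | 1.50 |

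These are the lowest values for each g. Where only disorders found at first trimester screening are excluded, genetic cases found later remain and the shift is smaller.

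**5. Other mismatches.** A 1-year window against one reaching to the sixth birthday lowers the SPR. A registry total prevalence that counts terminations and fetal deaths, set against a per-live-birth figure, tends to raise it. The documents give no numbers for either.

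**The case against.** The comparison is secondary and is described as descriptive: the Abstract rules out statistical inference from it, Section 9.2.1.1 treats it as context, and Section 9.7.2.5.2 itself warns that external adjustment is limited. The powered analysis uses the internal comparator, with the same definitions and follow-up in both cohorts. Section 9.7.2.5.2 names the right method and defines the SPR correctly as observed over expected, so its distributions may be loose wording for prevalences by category. Leaving the crude rate's population unnamed is an ambiguity, not an instruction to use the registry's. Section 9.7.2.6 also plans a malformation analysis that keeps women with any screening finding, which moves the registry closer to MACDP's definition.

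Most of this stands, and it lowers the importance of the point. It does not repair the text. The expected-count sentence is wrong on any literal reading, a risk ratio with a confidence interval will still be reported, and the sensitivity analysis is not tied to the external comparison.

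A reader might infer that the external comparison as a whole leans towards safety and would hide a real excess. The documents do not support that. The formula error can raise the SPR, as in the first example. Total prevalence pushes upward, the genetic exclusion may be only partial, and the internal comparison remains as the main safeguard.

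**Conclusion.** The point holds as something that should be corrected, not as a threat to the primary analysis. Section 9.7.2.5.2 states an invalid expected count, leaves the SPR multiplier unidentified, and standardizes on a post-exposure variable whose numerical effect is probably small.

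The case-definition mismatch is the most substantial part. It multiplies the SPR by (1 − g), giving 0.95 to 0.75 for a drug with no effect, on two assumptions: g between 5% and 25%, and complete removal of genetic cases from the registry. Under the narrower exclusion in Sections 4, 9.7.1.2 and 9.7.2.1 the bias is smaller. The follow-up gap leans the same way and the prevalence measure leans the other way, so the net direction is not established.

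**What to change.** Rewrite the paragraph in Section 9.7.2.5.2:

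- Expected = sum over maternal age and race/ethnicity strata of (registry births in the stratum × MACDP prevalence in that stratum); SPR = observed / expected.
- Adjusted prevalence = SPR × MACDP crude prevalence, with MACDP named.
- Drop gestational age as a standardizing variable.
- Use one case definition on both sides: take chromosomal and genetic defects out of the MACDP numerator, or restore them to the registry's for this comparison. Reconcile Table 2 with the exclusion wording in Sections 4, 9.7.1.2 and 9.7.2.1.
- Use the registry's prevalence at birth, and report the 1-year v sixth-birthday ascertainment gap beside the SPR.

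The cost is a paragraph of wording and some re-tabulation of aggregate MACDP counts, with no new data collection. It depends on published reports giving prevalence by stratum and by type of defect. Where they do not, that limit should be stated with the result.

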#### **9.7.2.6 Sensitivity Analysis**

Sensitivity analyses will be performed on both the erenumab-aooe exposed and internal comparator cohorts if sufficient sample size allows, and include but are not limited to the following:

- A sensitivity analysis of major congenital malformations will include women who have received any prenatal screening, regardless of the findings.
- A sensitivity analysis of major congenital malformations will include women where the result is known, regardless of the findings, prior to enrollment in the registry. Subsequently, a sensitivity analysis of major congenital malformations will include women who received any first trimester prenatal screening before enrollment where the result is known to be negative (see [Table 2](#)).
- Sensitivity analyses will also be conducted to study the effects of the timing of erenumab-aooe exposure before and during pregnancy and cumulative exposure periods on each outcome.
- A sensitivity analysis of major and minor congenital malformations will be performed that analyzes different cut points of exposure to erenumab-aooe, accounting for each trimester of exposure. While the primary cut point will be the date of LMP to the end of the first trimester (14 weeks gestation), additional sensitivity cut points will include: 16 weeks prior to LMP through the end of the first trimester, LMP date to the end of pregnancy, 16 weeks prior to LMP to the end of pregnancy, second trimester exposure only, and third trimester exposure only.
- Spontaneous abortions defined as occurring before 22 weeks gestation will also be examined in a sensitivity analysis to account for global variation in the definition for this outcome.
- A sensitivity analysis will be performed to examine the impact of time-varying exposure on primary and secondary outcomes. A time-varying exposure cox regression model will adjust for fixed covariates such as maternal age, presence of comorbidities, previous history of obstetric complications, and gestational age at exposure as time varying covariate. Details will be provided in the SAP.
- For spontaneous abortion, a sensitivity analysis will be performed based on gestational age at enrollment.

Sensitivity analyses may rely on sufficient sample sizes in order to execute. Full details will be described in the SAP.

#### 9.7.2.6.1 Subgroup Analysis

Additional subgroups of interest may be explored beyond what is outlined, below. If the difference in subgroups is meaningful, these covariates will be considered for adjustment of confounding in the primary analysis.

- Women in the internal comparator cohort who are migraine treatment naive will be examined separately with respect to the primary and secondary outcomes.
- Both the erenumab-aooe exposed and internal comparator cohorts will be summarized for primary and secondary outcomes both overall and by the subgroups of following parameters, if sufficient sample size allows:
  - Maternal age category
  - Race/ethnicity
  - Smoking status
  - Other classes of migraine therapy used during pregnancy and/or lactation during the infant's first year of life (among live births)
  - Type of migraine: episodic, chronic (with or without aura)
  - Severity of migraine: measured in terms of frequency (occurrence daily, weekly, monthly), time since the date of diagnosis, and presence of aura (ever vs. never), number of prior preventive migraine treatment failures (pre-pregnancy), days of acute migraine treatments each month (pre-pregnancy and by trimester)

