### 8.2 Secondary

Secondary objectives include the following:

- In women exposed to erenumab-aooe during pregnancy,
  - To estimate the proportion of pregnancy complications
  - To estimate the proportion of spontaneous abortion, still birth, elective termination, and preterm birth
- In infants of women exposed to erenumab-aooe during pregnancy,
  - To estimate the proportion of small-for-gestational age
  - To estimate the proportion of minor congenital malformations
  - To estimate the proportion of postnatal growth and development deficiency through the first year of life
- To compare the proportion of maternal, fetal, and infant outcomes of women with migraine exposed to erenumab-aooe consisting of women with migraine who have not been exposed to erenumab-aooe before or during pregnancy (internal comparator)
- To compare the frequency of major congenital malformations of women with migraine exposed to erenumab-aooe during pregnancy with women representing the prevalence of birth defects in the general population (external comparator)

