### 9.2.8 Study Follow-up

Women will be followed from enrollment through the end of their pregnancy and infants will be followed through 1 year after birth. Specific data to be collected during different periods during the follow-up are detailed below. Safety reporting will be ongoing throughout the duration of the study.

---

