### **At Delivery (estimated within 4 weeks of delivery date)**

- Reporter of information (eg, patient, PCP, OB, neurologist [indication specialist], nurse midwife, infant HCP, other)
- Pregnancy outcome (eg, live birth, stillbirth, spontaneous abortion, elective or therapeutic termination)
- Reason for elective or therapeutic termination (eg, prenatal testing finding, risk to mother's health, undesired pregnancy), if applicable
- Autopsy results and pathology reports, if available
- Mode of birth (vaginal delivery, assisted delivery/cesarean section, type of anesthesia)
- Number of migraines since last follow-up; number of migraines requiring treatment, and any prescription migraine treatments
- Changes in comorbid conditions

- Erenumab-aooe treatment (including start and stop dates, dose, dosing frequency, reason for discontinuation [if applicable])
- Current medications, including start and stop dates (eg, any other OTC migraine treatment(s), folic acid and other vitamins, herbal remedies or supplements, vaccinations, or other medications used to treat chronic conditions or comorbidities)
- Changes in lifestyle risk factors (eg, smoking, caffeine consumption, alcohol use, illicit drug use)
- Patient AEs and SAEs (including event, start date, ongoing or end date, seriousness, severity, relationship to erenumab-aooe, outcome, action taken)
- Infant characteristics:
  - Gestational age at birth
  - Sex
  - Birth weight
  - Length
  - Head circumference
  - Birth order (for multiple births), and number of fetuses
  - Apgar scores (1, 5, and 10 minutes)
  - Congenital malformations noted (including description and attribution)
  - Vaccination information
  - Whether infant is breastfed
  - Infant medication(s)
  - Infant AEs and SAEs (including event, start date, ongoing or end date, seriousness, severity, relationship to erenumab-aooe, outcome, action taken)

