**Infant Follow-up (estimated at 12, 26 and 52 weeks of age)**

- Reporter of information (eg, patient, PCP, OB, neurologist [indication specialist], nurse midwife, infant HCP, other)
- Feeding behavior (including breastfeeding)
- Weight
- Length
- Head circumference
- Postnatal growth and development (ie, social/emotional, language/communication, neurocognitive, movement/physical development milestones)
- Breastfeeding status
- Evidence of any new congenital malformations and growth alterations since last follow-up
- Vaccination information
- Patient and infant AEs and SAEs (including event, start date, ongoing or end date, seriousness, severity, relationship to erenumab-aooe, outcome, action taken)

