#### **Expected contacts with patient:**

- Enrollment
- End of Trimester 1 (approximately 14 gestational weeks)
- Mid-Trimester 2 (approximately 21 gestational weeks)
- Mid-Trimester 3 (approximately 34 gestational weeks)
- EDD plus 4 weeks
- Birth plus 12 weeks, 26 weeks, and 52 weeks (live births only)

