**Appendix E. Data Collection Overview (as per Standard of Care)**

Data Collection a	Enrollment	Prenatal Follow-Up			Pregnancy Outcome	Pediatric Follow-Up	Early Termination Visit
		End First Trimester (~14 weeks)	Mid Second Trimester (~21 weeks)	Mid Third Trimester (~34 weeks)	~4 weeks after EDD	Infant Age 12, 26, and 52 Weeks	End of Patient Participation in Study
Informed consent b	X						
Reporter of information c	X	X	X	X	X	X	X
Inclusion/exclusion criteria	X						
Patient demographics and characteristics d	X	X	X	X			
Medical history e	X						
Pregnancy history, and current pregnancy information f	X						
Lifestyle factors g	X	X	X	X	X		
Prior and concomitant medications h	X	X	X	X	X		
Erenumab-aooe prescription information i	X	X	X	X	X		X
Comorbid conditions	X	X	X	X	X		
Migraine and treatment status j		X	X	X	X		
Current pregnancy status		X	X	X			X k
Gestational age (weeks)	X	X	X	X	X		X k
Pregnancy outcome l		X	X	X	X		X k
Infant characteristics					X m	X n	X k
Infant abnormalities o					X	X	X k
Patient/infant AEs and SAEs p	X ----->						
Reason for early termination							X

Footnotes defined on next page of table.

AE = adverse event; EDD = estimated date of delivery; HCP = healthcare provider; IRB = Institutional Review Board; LMP = last menstrual period; OB = obstetrician;  
OTC = over the counter; PCP = primary care physician; SAE = serious adverse event

a Available data will be collected; no additional diagnostic or monitoring procedures shall be applied to the patients outside of routine clinical practice.

b Written or verbal informed consent must be obtained before any data collection (per local regulations or IRB requirements). If the patient is a minor, written consent must be obtained from the parent or legal guardian.

c Including the patient, PCP, OB, neurologist [indication specialist], nurse midwife, infant HCP, other)

d Including age of mother, education level, race/ethnicity, height, and pre-pregnancy and current pregnancy weight.

e Including surgical and medical history/significant maternal medical conditions other than migraine; migraine history; family reproductive history

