**Table 4. Pediatric Follow-up (approximately at infant age 12, 26, and 52 weeks after birth)**

Variable Category	Data Elements	Additional Information
Date of Contact	Date	
Reporter of Information a	Patient	Contact information (any changes); Secondary contact (if available)
	PCP	Contact information (any changes)
	Neurologist (indication specialist)	Contact information (any changes)
	Infant HCP	Contact information (any changes)
	Other (please specify)	Contact information (any changes)
Infant Vaccinations Received since Last Contact	Vaccination and date (with calendar to aid recall)	
Infant Characteristics	Length	Value and percentile score
	Head circumference	Value and percentile score
	Weight	Value and percentile score
	Infant feeding: breastfed, formula, combination breastfed/formula, other (please describe)	Number of weeks exclusively breastfed since birth
	Infant developmental milestones: social/emotional, language/communication, cognitive, movement/physical development milestones	Any identified developmental delays or impairment? If yes, please characterize
	Any new malformation or growth alterations since last visit	Including description and attribution

Footnotes defined on last page of the table

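### Maternal drug use is not scheduled for collection at the 12-, 26- and 52-week infant contacts, so the lactation part of a planned subgroup cannot be formed beyond the first weeks after birth

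*Protocol*

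**What the plan says.** The analysis side of the protocol needs maternal drug data through infancy. Section 9.7.2.6.1 lists, among the subgroups for primary and secondary outcomes in both cohorts, "Other classes of migraine therapy used during pregnancy and/or lactation during the infant's first year of life (among live births"), if sample size allows. Section 8.2 has the secondary objective "To estimate the proportion of postnatal growth and development deficiency through the first year of life", and infant outcomes are also compared with the internal comparator. Section 9.1 states in general terms that migraine treatment and other therapeutic exposures will be collected during pregnancy and through one year after birth.

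The collection side is set out in Section 9.2.8, which says "Specific data to be collected during different periods during the follow-up are detailed below". At the delivery contact it lists erenumab treatment and "Current medications, including start and stop dates (eg, any other OTC migraine treatment(s"). Section 9.4.2 times that contact at "EDD plus 4 weeks". At the infant contacts it lists "Feeding behavior (including breastfeeding"), growth, development, new malformations, vaccination and adverse events, and no maternal drug item. Appendix F Table 4 follows the same pattern: it asks for "Number of weeks exclusively breastfed since birth" but not for what the mother was taking.

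**The concern.** A subgroup defined by drug use during lactation needs drug dates that overlap the period of breastfeeding. The plan follows breastfeeding through the year but stops recording maternal drugs shortly after delivery. No statistical analysis plan can recover a variable that was never collected, so this has to be settled in the protocol and the eCRF.

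The same gap bears on a second analysis. Cohort membership (Section 9.3.1) is decided by exposure up to the end of pregnancy. A comparator mother may start erenumab after delivery, and an exposed mother who stopped may resume it. Either may breastfeed, and the scheduled infant contacts would not record the drug. A one-year difference in growth or development, or the lack of one, would then be read as a pregnancy-exposure result although some infants may also have been exposed through milk. Section 7.2 itself names lactation as an area without adequate studies.

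**Working it through.** The point rests on no sample-size, power or alpha figure. The check sets the lists side by side and then counts the weeks covered.

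**Step 1. Where maternal drug use is listed.**

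| Source | Delivery contact | 12, 26 and 52 weeks | Early termination contact |
|---|---|---|---|
| Section 9.2.8 | Erenumab and current medications | Neither | Erenumab and current medications |
| Appendix E, erenumab row | Marked | Blank | Marked |
| Appendix E, medication row | Marked | Blank | Blank |
| Appendix E, migraine and treatment row | Marked | Blank | Blank |
| Appendix F | Table 3: erenumab and medications | Table 4: neither | Table 5: erenumab only |

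The erenumab row of Appendix E reads "Erenumab-aooe prescription information i X X X X X X". That is six marks across seven columns, and the empty column is pediatric follow-up. All three sources agree that no maternal drug item is scheduled at the infant contacts, so this is not a slip in one table.

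**Step 2. How much of the first year is covered.** Inputs: the due date corresponds to 40 weeks of gestation; the last scheduled drug record is at the due date plus 4 weeks, that is 44 weeks; the window is 52 weeks from birth.

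Weeks covered = 44 − gestational age at birth. Weeks uncovered = 52 − weeks covered.

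- Birth at 34 weeks: 44 − 34 = 10 covered, 42 uncovered (42/52 = 81%).
- Birth at 37 weeks: 44 − 37 = 7 covered, 45 uncovered (87%).
- Birth at 40 weeks: 44 − 40 = 4 covered, 48 uncovered (92%).
- Birth at 42 weeks: 44 − 42 = 2 covered, 50 uncovered (96%).

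Section 9.2.8 describes the delivery contact as falling within 4 weeks of the delivery date itself. On that timing at most 4 weeks are covered and at least 48 are not, whatever the gestational age.

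**Step 3. What can still be analysed.** The pregnancy part of the subgroup is fully collected. Drug use and feeding in the first weeks are recorded at the delivery contact. Feeding is recorded through the year, so never-breastfed infants can be identified and treated as exposed in utero only. What is missing is maternal drug use in breastfeeding mothers after the delivery contact.

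**The case against.** Several counter-arguments have weight.

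- **The protocol does promise the data.** Section 9.1 says migraine treatment exposures are collected through one year, and Appendix F says its variables may change. This stands as far as it goes: the fault is a contradiction to be reconciled, not an outright decision against collection. But the detailed lists are what the eCRF would be built from, and they agree with each other.
- **The early termination form may fill the gap.** Its Appendix E column refers to the end of participation, and its status options include completed follow-up, so completers might also give erenumab dates there. Section 9.2.8, however, describes the contact as one of early termination, made only if applicable. A reader might infer that post-partum erenumab is recorded for leavers only; the documents leave this unclear. On either reading, Appendix E and Appendix F Table 5 have no field there for the mother's other drugs, and those are what the quoted subgroup concerns.
- **Lactation exposure is reportable as a safety finding (Section 11.1.3).** True, so it would be wrong to say that nothing could record it. But this is event reporting on the sponsor's product, not systematic exposure data on both cohorts and all migraine drugs.
- **No objective concerns lactation, and Section 9.7.2.2 limits collection to data aligned with the objectives.** Fair, and a reason why deleting the subgroup is an acceptable alternative. It does not remove the interpretive limit on the one-year outcome, which is an objective.
- **The subgroup is conditional on sample size.** No sample size supplies an uncollected variable.

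**Conclusion.** The contradiction is real. Followed as written, the schedules leave roughly 80% to 96% of the infant's first year without a scheduled maternal drug record, for births between 34 and 42 weeks. The lactation part of the subgroup cannot be formed beyond the first weeks, and among breastfed infants the one-year growth and development comparison cannot distinguish exposure in utero from exposure through milk. This assumes that the lists in Section 9.2.8 and Appendices E and F, not the general sentence in Section 9.1, determine what is collected.

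Three stronger readings should be resisted. A reader might infer that the two routes of exposure cannot be separated in any infant; the feeding data identify never-breastfed infants, so this goes too far. A reader might infer that post-partum use is commoner in the exposed cohort and attach a risk ratio to the bias; the documents give no rate of post-partum use and no lactation effect, so neither the direction nor the size is known. And a reader might extend the point to the main result; the primary malformation analysis rests on first-trimester exposure and is unaffected. The consequence is confined to secondary analyses.

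**What to change.** Add the existing erenumab block and the migraine-medication block (names, start and stop dates), completed for the mother in both cohorts, to the 12-, 26- and 52-week contacts in Section 9.2.8, the pediatric column of Appendix E and Appendix F Table 4. Reconcile these with Sections 9.1 and 9.7.2.6.1. State whether the early termination form is also completed by women who finish follow-up, and align its medication items across Section 9.2.8, Appendix E and Appendix F Table 5.

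Report growth and development descriptively by lactation exposure. Label any analysis restricted to infants without lactation exposure as a sensitivity analysis, and say that it conditions on a post-birth variable: breastfeeding and resumption of treatment may track migraine severity, so the restriction can introduce selection of its own.

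If the fields are not added, delete the lactation part of the subgroup, correct Section 9.1, and state the limitation on the one-year comparison.

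The cost is a few more data fields at three contacts that Section 9.4.2 already schedules with the patient. No new contact or procedure is needed. Once infants have passed these contacts, the information could be recovered only by recall, so the change is best made early.
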